6.1.7.8. Adverse Event Follow-Up

All non-serious AEs that are not related or unlikely to be related to study treatment will be followed until the end of study participation. All SAEs or AEs that are considered as possibly, probably, or definitely related to treatment will be followed until resolution or stabilization.

6.1.7.9. Special Considerations

Cannabidiol inhibits drug metabolism mediated by a subset of CYP proteins (see Section Section 1.1.2). Thus, the investigator and study center staff should monitor patients who are taking concomitant medications that are metabolized by CYP2C19, CYP2C9, CYP2D6, CYP3A4, CYP1A2, or by P-glycoprotein with special care.

6.2. Efficacy Assessment

The HQ-CT will be completed at the Study Completion/Early Withdrawal. The questionnaire assesses food-related problem behaviors and consists of three factors: Hyperphagic Drive (internal consistency 0.76), Hyperphagic Behavior (internal consistency 0.80) and Hyperphagic Severity (internal consistency 0.60). It is a 13-item parent completed questionnaire (Fehnel et al., 2015).

7. STUDY PROCEDURES

Prior to performing any study related procedures or assessments, the Investigator will ensure that the patients and/or their parent(s)/caregiver(s) (if applicable) provide written informed consent and that the perdiatric patient provides assent (as appropriate). Patients and their parent(s)/caregiver(s) (if applicable) will receive a copy of the informed consent form (ICF) and asent form for review and must provide fully informed consent prior to study participation.

The consent process must be conducted and the ICF signed before any study procedures. See Section 11.4 for guidelines regarding patient consent and assent.

The assessments and procedures that will be conducted during this study are summarized in Table 1.

7.1. Safety Period

7.1.1. Visit 1 (Day 1)

The following procedures and assessments will be performed:

- Obtain written informed consent/assent (if appropriate).
- Review of inclusion and exclusion assessment.
- Review/assess concomitant medications.
- Record vital signs (seated blood pressure, pulse rate, temperature, and respiration rate).
- Collect blood samples for clinical labs (chemistry and hematology)
- Collect urine sample for urinalysis, urine drug screen, and urine dipstick pregnancy test (all female patients of childbearing potential).
- Perform resting 12-lead ECG.
- Perform physical examinations.
- Record weight.
- Dispense CBD.
- Perform drug accountability.
- Review AEs.

7.1.2. Monthly (Visits 2, 3, and 4) and Quarterly (Visits 5, and 6) Visits

The following procedures and assessments will be performed:

- Review/assess concomitant medications.
- Record vital signs (seated blood pressure, pulse rate, temperature, and respiration rate).
- Collect blood samples for clinical labs (chemistry and hematology)
- Perform resting 12-lead ECG.

- Perform physical examinations.
- Record weight.
- Collect/review/dispense CBD.
- Perform drug accountability.
- Review AEs.

7.2. End of Study (Visit 7) or Early Withdrawal

The following procedures and assessments will be performed:

- Review/assess concomitant medications.
- Record vital signs (seated blood pressure, pulse rate, temperature, and respiration rate).
- Collect blood samples for clinical labs (chemistry and hematology)
- Collect urine sample for urinalysis, urine drug screen, and urine dipstick pregnancy test (all female patients of childbearing potential).
- Perform resting 12-lead ECG.
- Perform physical examinations.
- Record weight.
- Complete the HQ-CT.
- Collect/review CBD.
- Perform drug accountability.
- Review AEs.
- Dispense CBD for Taper Period.

End of Study assessments (If the patient withdraws prematurely from the Safety Period, all Visit 7 (End of Study) procedures should be conducted. Site staff will follow-up with the patient 4 weeks after completion of study via the telephone to collect information regarding AEs and concomitant medications.

7.3. Taper Period (Visit 8)

The following procedures and assessments will be performed:

- Collect CBD.
- Review concomitant medication and AEs.

7.4. Follow-Up Period (Visit 9)

The following assessments will be performed by phone call 30 days after Visit 7 (End of Study):

• Review/assess concomitant medications and review AEs.

8. STATISTICS

8.1. Safety Endpoints

Changes in safety endpoints will be reported as mean/median change from baseline at relevant time points and as a listing of events that fall outside normal limits. Baseline is defined as Visit 10 of INS011-16-085.

- Incidence, type, and severity of AEs and serious adverse events (SAEs) associated with Cannabidiol Oral Solution (i.e., treatment-emergent adverse events [TEAEs]).
- Changes from baseline in vital signs, physical exam, ECG findings, and laboratory values (hematology, chemistry, and urinalysis).
- Change from baseline in weight.

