- Incidence, type, and severity of AEs and serious adverse events (SAEs) associated with Cannabidiol Oral Solution (i.e., treatment-emergent adverse events [TEAEs]).
- Changes from baseline in vital signs, ECG findings, and laboratory values (hematology, chemistry, and urinalysis).
- Change from baseline in weight.

Exploratory Efficacy Endpoint

• Change in total score of the HQ-CT from Baseline to Study Completion/Early Withdrawal.

Baseline is defined as Visit 10 of INS011-16-085.

Statistical Methods:

Safety Analysis

All safety assessments, including AEs, clinical laboratory evaluations, vital signs, 12-lead ECGs, and physical examination (including weight) will be listed for each visit. When appropriate, they will be summarized with descriptive statistics by age and dose cohort. The Medical Dictionary for Regulatory Activities (MedDRA; Version 20.0 or higher) will be used to classify all adverse events with respect to system organ class and preferred term. Adverse event summaries will include only TEAEs, which will be summarized for each treatment group.

- Clinical laboratory findings and vital signs will be summarized for all patients for observed values and change from baseline. Shifts from baseline to outside normal range criteria will also be presented for all patients.
- Weight will be listed and summarized for all patients for observed values and change from baseline. Shifts from baseline to outside normal range criteria will also be presented for all patients.
- Results of physical examinations conducted throughout the study will be presented in listings and summarized descriptively. Shifts from baseline according to normal and abnormal criteria will also be presented for all patients.
- Concomitant medications will be reported in the data listings.
- Statistical analyses will be performed using SAS® (Version 9.3 or higher, SAS Institute Inc.) or R (Version 3.3 or higher, Roswell Park Cancer Institute).

Missing Data

There will be no imputation of the missing values. All assessments will be conducted based on all the observed data.

Table 1: Schedule of Events

ASSESSMENTS SAFETY PERIOD			TAPER PERIOD	FOLLOW-UP PERIOD ^g			
Visit Number	1ª	2, 3, 4 (monthly)	5, 6 7 Early (quarterly) (End of Study) Withdrawal 8		Dai iy		9 (Phone Call)
Study Time Points	Day 1	Weeks 4, 8, 12	Weeks 24, 36	Week 48		0-6 Days	30 Days After EOS
Visit Window (Days)	± 5	± 5	± 5	± 3		± 3	± 5
Informed consent **	X			^			

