3. INVESTIGATIONAL PLAN

3.1. Overall Study Design

This is a multicenter, open-label study designed to assess long-term safety and tolerability of CBD in patients with Prader-Willi Syndrome. Patients must have completed INS011-16-085 to be eligible.

The investigator will ensure that the patients legal representative [parent(s)/caregiver(s)] will receive a copy of the informed consent form for review and provide full informed consent prior to study participation. Patients may enroll in this long-term safety study (INS011-17-115) after completing INS011-16-085 Visit 10 (Study Completion) to avoid interruption of the investigational product. Patients will have up to 2 weeks to enroll in INS011-17-115.

Patients will receive CBD treatment for approximately 48 weeks. Total daily doses ranging from 20 mg/kg/day to 40 mg/kg/day will be administered with standard meal. If any participant does not enroll within the 2 week window, that patient will not be eligible to enroll into the study.

The study will consist of a Safety Period (48±2 weeks), Taper Period (6±3 days), and a Follow-up Period (30±5 days). Treatment visits will be scheduled monthly for the first 3 months and then quarterly over the remaining 9 months. All patients will complete a Visit 7 (End of Study) or Early Withdrawal Visit regardless of when they stop treatment/complete the study. A Follow-Up telephone call (Visit 9) will occur 30 days after the end of either the End of Study (Visit 7) or Early Withdrawal.

Once the informed consent for INS011-17-115 is provided within the required time frame, the patient will receive a total daily dose ranging from 20mg/kg/day to 40mg/kg/day.

Patients will be dosed approximately every 12 hours with food to help ensure consistent plasma levels are achieved. Patients will be dosed for 48 weeks during which the investigator will assess safety and tolerability.

The study will be terminated upon one of the following:

- The investigational product is successfully approved for marketing in the US.
- Sponsor elects to terminate INS011-17-115.
- The patient has received 48 weeks of treatment.

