3.2.2. Exclusion Criteria

Patients will be excluded for any of the following:

- 1. Patient or parent(s)/caregiver(s) have daily commitments during the study duration that would interfere with attending all study visits.
- 2. Experienced an anoxic episode related to study drug requiring resuscitation during their previous study.
- 3. Uncontrolled Type I and Type II diabetes.

- 4. Developed an adverse event thought to be related to CBD in the previous study and for whom the Investigator determines that continuing treatment with CBD would not be in the best interest of the patient.
- 5. History of clinically significant gastrointestinal, renal, hepatic, neurologic, hematologic, endocrine, oncologic, pulmonary, immunologic, psychiatric, or cardiovascular disease, or other condition which would jeopardize safety or impact validity of results (per investigator).
- 6. Currently taking felbamate.
- 7. Compromised respiratory function or severe respiratory insufficiency.
- 8. Pregnant or lactating female.
- 9. In the opinion of the investigator, the patient is unsuitable in any other way to participate in this study.

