6.1 General Principles

All data processing, summarization and analyses will be performed using Covance's SAS Environment / Version 9.4 (or later) of the SAS® statistical software package.

The analysis treatment group will be defined by the modal dose of study drug (dose of the study drug that the patient took for the longest period).

The following principles will be applied to all TFLs unless otherwise stated:

Principle	Value		
Significant tests	Two-sided and use a 5% significance level		
Treatment group labels	Listings:		
and order presented	Cannabidiol Oral Solution (20mg/kg/day)		
	Cannabidiol Oral Solution (30 mg/kg/day)		
	Cannabidiol Oral Solution (40 mg/kg/day)		
	Tables:		
	CBD (20 mg/kg/day)		
	CBD (30 mg/kg/day)		
	CBD (40 mg/kg/day)		
	All CBD		
Tables	Data in summary tables presented by treatment group and visit (where applicable)		
Listings	All data collected presented by		
	Treatment group		
	Patient		
	Visit (where applicable)		
	Date;		
	unless otherwise specified		
Descriptive summary	Number of patients/observations (n)		
statistics for continuous variables	Mean		
	Standard deviation (SD)		

Sponsor Name: Insys Development Company, Inc.

Sponsor Protocol ID: INS011-17-115 Covance Study ID: 000000163385

Principle	Value
	Median
	Minimum
	Maximum
Descriptive summary statistics for categorical variables	Frequency counts and percentages [n (%)]
Denominator for percentages	Number of patients in the analysis population, unless stated otherwise in table shell(s)
Include "Missing" as	Yes, when the number missing is greater than zero for at
category	least one treatment group
Display for 0	Leave blank
percentages	
Display to one more decimal place than collected value	Mean Mean Difference
	Median Percentages
Display to two more	Standard Deviation
decimal places than collected value	Confidence Interval
Limit of precision for displays	3 decimal places

Baseline is defined as Visit 10 of INS011-16-085.

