6.4.2 Prior and Concomitant Medications

Medications received prior to or concomitantly with treatment will be coded by Covance using the WHO Drug Dictionary [Version March 2018 (or a later version if updated during the study)], Anatomical Therapeutic Chemical (ATC) Classification codes.

Prior medications and concomitant medications are defined as follows:

Prior medications are those prior to the first dose date of IMP treatment on INS011-16-085.

Sponsor Name: Insys Development Company, Inc.

Sponsor Protocol ID: INS011-17-115 Covance Study ID: 000000163385

Concomitant medications are those with a start date on or after the first dose date of IMP treatment on INS011-16-085, or those with a start date before the first dose date of IMP treatment and a stop date on or after the first dose date of IMP treatment or ongoing end of study.

If a medication cannot be classified as "prior" or "concomitant" after applying imputation rules for missing/incomplete dates, it will be classified as concomitant.

Prior medications and concomitant medications will be listed together and summarized separately for enrolled population.

The number and percentage of patients using each medication will be displayed together with the number and percentage of patients using at least one medication within each therapeutic class (ATC-Level 2), chemical subgroup (ATC-Level 4), and generic term.

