6.7.2 Adverse Events

All AEs recorded on the eCRF will be coded using the MedDRA dictionary [Version 21.1 (or a later version if updated during the study)] and classified as treatment – emergent AEs (TEAEs) as follows:

• TEAEs are events with start date on or after the date of first dose of IMP and up to 14 days after the last dose of IMP or events with start date prior to the date of first dose of IMP whose severity worsens on or after the date of first dose of IMP on INSO11-17-115.

All AE data will be listed by treatment group. Treatment-emergence status will be flagged in the listing. In addition, corresponding listings of treatment-emergent serious AEs (TESAEs), AEs leading to permanent discontinuation of IMP and AEs resulting in death will be produced. AE ongoing or worsened from INS011-16-085 will be listed.

Summary tables of TEAEs by treatment group and overall will be produced for the enrolled population. No statistical comparisons of AEs between treatment groups will be performed.

The severity of all AEs is recorded as mild, moderate, or severe. If severity is missing for a TEAE, it will be considered severe.

The relationship between an AE and IMP treatment is assessed as definite, probable, possible, unlikely or not related. A treatment-related AE is an AE considered by the investigator as definitely, possibly, or probably related to IMP treatment or with unknown/missing relationship to IMP treatment.

An overview table will summarize the number and percentage of patients with at least one of the following TEAEs, where patients with more than one TEAE in a particular category are counted only once in that category:

Sponsor Name: Insys Development Company, Inc.

Sponsor Protocol ID: INS011-17-115 Covance Study ID: 000000163385

- any TEAE;
- TEAE by severity (mild, moderate, severe);
- treatment-related TEAE;
- severe treatment-related TEAE;
- TESAE;
- TESAE by severity;
- treatment-related TESAE;
- TEAE leading to study drug discontinuation.

The overview table will be repeated to summarize the number of TEAEs (displaying the number and percentage of observed events).

The number and percentage of patients reporting each AE will be summarized by System Organ Class (SOC) and Preferred Term (PT) for all enrolled patients. Tables will be sorted alphabetically by SOC. PTs will be sorted by descending overall total. The following summaries will be produced:

- TEAEs, by SOC and PT;
- TEAEs related to IMP treatment, by SOC and PT;

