6.7.3 Laboratory Evaluations

6.7.3.1 Standard Safety Laboratory Panel

Data for the following hematology, blood chemistry, and urinalysis analytes received from central laboratory will be listed and summarized by treatment group and visit. If data for any additional analytes are also received or recorded, then these will be listed only.

Hematology	Serum Chemistry	Urinalysis
Hemoglobin	Albumin	pH
Hematocrit	Blood Urea Nitrogen	Specific Gravity
Total Leukocyte Count	Creatinine	Protein
Differential Leukocyte Count	Total Bilirubin	Glucose
Red Blood Cell Count	Alkaline Phosphatase (ALP)	Ketones
Platelets	Aspartate Transaminase (AST)	Bilirubin
Neutrophils (abs, %)	Alanine Transaminase (ALT)	Blood
Lymphocytes (abs, %)	Sodium	Nitrite
Monocytes (abs, %)	Potassium	Leukocyte Esterase
Eosinophils (abs, %)	Chloride	Urobilinogen
Basophils (abs, %)	Lactate Dehydrogenase (LDH)	Color and Clarity
White Blood Count	Uric Acid	Microscopic
	Glucose Calcium	Urine T. Protein, Random
	Çaldani	Urine Creatinine, Random

All laboratory data will be reported in conventional units. Out-of-reference-range values will be flagged as high (H) or low (L) in the listings.

For analysis purposes, values preceded by a "<" or a ">"sign (i.e. those below or above the limits of quantification) will be considered equal to the lower or upper limit of quantification, respectively.

Laboratory and urinalysis data will be summarized by visit using standard descriptive statistics for the enrolled population. Changes from baseline will also be summarized.

For hematology and serum chemistry, shift tables presenting movement in and out of reference ranges from baseline to each scheduled post-baseline visit will be

Sponsor Name: Insys Development Company, Inc.

Sponsor Protocol ID: INS011-17-115 Covance Study ID: 000000163385

provided for each treatment group. Corresponding shift tables will be produced for urinalysis.

6.7.3.2 **Urine Drug Screen**

A urine sample for the following assessments will be collected at study entry and end of study/early withdrawal: amphetamines, barbiturates, benzodiazepines, cocaine, opiates, phencyclidine and tetrahydrocannabinol.

Results from the urine drug screen will be listed for the enrolled population.

6.7.3.3 **Urine Pregnancy Test**

A urine dipstick pregnancy test will be performed on all female post-menarchal patients at Visit 1 and Visit 7 (End of Study) or early withdrawal.

Pregnancy screen results will be listed for the enrolled population.

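### Visit 10 of the parent trial is a sound baseline for change during the extension, but not for change since starting CBD; weight in kg cannot separate growth from a drug effect

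*Protocol*

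**What the plan says.** Protocol 8.1 states "Baseline is defined as Visit 10 of INS011-16-085", and SAP 6.1 repeats the definition. Under SAP 6.7.3 to 6.7.6, changes and shifts in laboratory values, vital signs (including weight), ECG and physical examination run from that point. For hematology and chemistry the SAP plans "shift tables presenting movement in and out of reference ranges from baseline to each scheduled post-baseline visit". Tables are laid out by modal dose group, plus an All CBD column, and by visit where applicable.

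On what Visit 10 represents, Protocol 3.1 lets patients enroll "after completing INS011-16-085 Visit 10 (Study Completion) to avoid interruption of the investigational product", within two weeks. Exclusion criterion 4 in Protocol 3.2.2 concerns a patient who "Developed an adverse event thought to be related to CBD in the previous study", but excludes that patient only if the investigator judges that continuing is not in the patient's interest.

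Two SAP provisions look back into the parent trial. SAP 6.7.2 says "AE ongoing or worsened from INS011-16-085 will be listed", and SAP 6.4.2 says "Prior medications are those prior to the first dose date of IMP treatment on INS011-16-085". Neither provides a change or shift table from a pre-CBD value.

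Change in weight is a named safety endpoint. SAP 6.7.4 summarises it in kg, alongside height and BMI, with shifts to outside a normal range that neither document defines for weight. The only mention of age in the safety summaries is in the Protocol synopsis: "When appropriate, they will be summarized with descriptive statistics by age and dose cohort". The SAP table layout does not carry it forward.

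**The concern.** The objective is the long-term safety of CBD. If CBD had already moved a laboratory, ECG, vital-sign or weight value by the end of the parent trial, tables that start there show only whether it moved further. A value already abnormal at Visit 10 falls in the abnormal-at-baseline row of the shift table and is not a new shift. If other entrants first receive CBD in this study, their change from Visit 10 is whole change, and the All CBD column averages it with added change without saying so.

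Weight raises a different problem. Children and adolescents gain weight as they grow, and the study has no control arm. A mean change in kg cannot be read as more or less than expected for age and sex.

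**Working it through.** The plan gives no figure to reproduce. The 66 in Protocol 8.3 is a roll-over maximum with no effect size, SD or power behind it. The check is therefore a reading of the text followed by illustrations on stated assumptions.

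**1. Was Visit 10 on treatment?** Protocol 3.1 speaks of avoiding a break in the investigational product. Exclusion criterion 4 shows that CBD was given in the parent trial and leaves room for exposed patients to enter. Prior exposure in some entrants is thus a reasonable inference, though not a stated fact. SAP 5.2 refers to double-blind treatment although this study is open-label. That may point to a blinded parent trial, but neither arms nor allocation are given.

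**2. Mean change.** Let p be the share of entrants given CBD in the parent trial and f the share of an effect already reached by Visit 10. Both are assumed, with the same full effect in everyone. Exposed patients show 1 − f of the effect and others show all of it:

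visible share = p(1 − f) + (1 − p) = 1 − p × f

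| p | f = 25% | f = 75% | f = 100% |
|---|---|---|---|
| 0 | 100% | 100% | 100% |
| 1/3 | 92% | 75% | 67% |
| 1/2 | 87.5% | 62.5% | 50% |
| 2/3 | 83% | 50% | 33% |
| 1 | 75% | 25% | 0% |

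**3. Shift tables.** Assume that q = 5% to 15% of exposed patients became abnormal on an analyte by Visit 10 and that r = 50% to 100% of those persist. With the maximum of 66 patients, the number held in the abnormal-at-baseline row is 66 × p × q × r:

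- p = 1/2: from 66 × 0.5 × 0.05 × 0.5 = 0.8 to 66 × 0.5 × 0.15 × 1 = 5.0 (4.95).
- p = 1: from 1.65 to 9.9.
- p = 0: none.

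**4. Weight.** The Safety Period is 48 ± 2 weeks and enrollment may take up to 2 weeks, so Visit 10 to Visit 7 spans 46 + 0 = 46 to 50 + 2 = 52 weeks. At an assumed 5 kg a year, growth adds 5 × 46/52 = 4.4 kg to 5 × 52/52 = 5.0 kg. For a fully grown patient it adds 0. For scale, Protocol 1.3 reports weight increases in the sponsor's long-term epilepsy study from a little over 2 lb to about 7 lb. At 0.4536 kg per lb that is about 0.9 to 3.2 kg. Assumed growth covers this range.

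**5. Age.** Protocol 1.3.1 gives 8 to 17 years, and Protocol 3.1.1 plans the C-SSRS for ages 7 to 17. The entry criteria set no age limit, and SAP 6.6.5 provides for adult C-SSRS assessments, so some adults are possible.

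**The case against.** The two documents agree on the baseline, and it answers a proper question: what changes during the extension. Most of the information also stays visible: observed values by visit, out-of-range flags, the abnormal-at-baseline rows and the listing of adverse events carried over from the parent trial. Safety is descriptive, with no inferential analysis. All of this stands, and it limits the point to the missing view of total change since before CBD.

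The parent design is not in the documents, so the illustration runs from no loss to complete loss and cannot by itself argue for a large problem. The pre-dose values may not be obtainable. These objections also stand.

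On weight, short stature (Protocol 1.4) and permitted growth hormone (Protocol 4.7.1) make weight-for-age hard to read alone. BMI is already summarised, and table shells not available here might define the normal range. The first objection is right and shapes the fix. Raw BMI does not remove the need for an age and sex standard in children.

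A reader might infer more: that Visit 10 is a wrong baseline, that every entrant was on CBD, or that abnormalities are concealed. The documents support none of these. Visit 10 is valid for added change, the exposed share is unknown, and a value abnormal at Visit 10 is displayed, only not counted as new. Nor do the short time to steady state or the early adverse events in the epilepsy studies (Protocol 1.3) show that CBD had moved any value in these patients by Visit 10.

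**Conclusion.** The point holds in a limited form. For entrants who took CBD in the parent trial, the planned tables show change since Visit 10, not since starting CBD. If there was a non-CBD arm, the All CBD column combines two kinds of baseline. This rests on inferred prior exposure, and the size of any loss is unknown. The percentages and counts above depend on assumed p, f, q and r and on the maximum enrollment of 66.

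The weight point does not depend on the parent trial. In patients expected to be mostly 8 to 17 years old, change in kg cannot separate growth from a drug effect. Its size depends on an age mix that the documents do not give; 0 to 5.0 kg is an assumed range. No test or sample-size statement is affected.

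**What to change.** **Baseline.** Keep Visit 10. In SAP 6.1, add supplementary change and shift tables for laboratory values, ECG, vital signs and weight from the last value before the first CBD dose in either study, where obtainable. If the parent trial had a non-CBD arm, split the All CBD column by parent treatment. If pre-dose values cannot be obtained, state that the tables show change since Visit 10 and not since starting CBD.

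**Weight.** In SAP 6.7.4, for patients under 18, add change from baseline in age- and sex-standardised BMI and weight z-scores. Read the two together because of short stature and growth hormone use. Name the growth reference and the shift cut-offs in the SAP before database lock. Keep the kg summaries, and use kg and BMI for adults.

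**Cost.** The cost is extra descriptive tables and a merge with parent data. The SAP already needs parent Visit 10 values and first-dose dates, but whether usable pre-dose values exist is not stated. Weight z-scores use age, sex and weight, which are already collected; BMI z-scores also need height. The split groups would be small: 66p and 66(1 − p) give 22/44, 33/33 or 44/22 for p = 1/3, 1/2 or 2/3. Only the All CBD column should therefore be split. Without a control arm the results stay descriptive.

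**Minor consistency items, separate from the main point.** Protocol 8.5.3.4 starts the ECG interpretation shifts at Screening; align it with the Baseline in Protocol 8.1 and SAP 6.7.5. Height is used in Protocol 8.5.3.5 and in SAP 6.4 and 6.7.4 but is missing from Table 1 footnote d and Protocol section 7; list it there.
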